7 RANDOMIZATION AND BLINDING PROCEDURES

Enrollment will occur after all Screening procedures have been performed and eligibility for the study is confirmed at Baseline. After Baseline, subjects will enter a 4-week randomized, DB, placebo-controlled phase. Subjects will be randomized at Baseline to take DB AMPH ER TAB (or matching placebo) orally once daily.

All study drug product samples will be supplied in identical containers and will be similar in physical characteristics (color, smell, flavor, and appearance), thereby enabling DB conditions.

Unblinding should occur only when knowing the treatment assignment has a bearing on the medical treatment or evaluation of a subject. Whenever possible, the need to unblind should be discussed with the Sponsor prior to unblinding. For emergency unblinding, study personnel will use the IWRS unblinding module.

Table 6 Sponsor's Contact Information for Unblinding Procedures

Contact	Phone number	Fax number
Tris Pharma, Inc		
[name] Director, Regulatory Affairs	Direct # [contact]	NA
[contact]		

A subsequent written report, including all pertinent details, must be submitted to the Sponsor within 24 hours of the unblinding. Whenever possible, the blind of the subject should be maintained.

If Investigator or site personnel or subject unblinded, the subject must be withdrawn from the study, and procedures accompanying withdrawal are to be performed.

Confidential Page 40 of 67

8 ADVERSE AND SERIOUS ADVERSE EVENTS

This section defines AEs and outlines the procedures for appropriately collecting, grading, recording, and reporting them. Information in this section complies with 21 Code of Federal Regulations (CFR) 312, ICH Guideline E2A: Clinical Safety Data Management: Definitions and Standards for Expedited Reporting, and ICH Guideline E6(R2): Good Clinical Practice.

The Investigator is responsible for the detection and documentation of events meeting the criteria and definition of an AE or SAE, as provided in this protocol. During the study, when there is a safety evaluation, the Investigator or site staff will be responsible for detecting AEs and SAEs, as detailed in this section of the protocol.

8.1 Definition of an Adverse Event

An AE is defined as any untoward medical occurrence in a subject, or clinical investigation subject administered a pharmaceutical product, whether or not the event has a causal relationship with this treatment.

An AE may be any unfavorable and unintended sign (including an abnormal laboratory finding), symptom, or disease temporally associated with the use of a study medication, whether or not considered causally associated with the use of the study medication. Any abnormal laboratory value deemed clinically significant by the Investigator, regardless of causal relationship, must be reported as an AE.

Examples of an AE include the following:

- significant or unexpected worsening or exacerbation of the condition or indication under study, taking into consideration the daily fluctuation of symptoms of ADHD.
- exacerbation of a chronic or intermittent pre-existing condition, including either an
 increase in frequency or intensity of the condition (e.g., abnormal physical examination
 finding)
- signs, symptoms, or clinical sequelae of a suspected interaction
- signs, symptoms, or clinical sequelae of a suspected overdose of the study medication or a concurrent medication (overdose per se should not be reported as an AE or SAE, unless non-serious or serious sequelae occur)

The following examples are not considered AEs:

- medical or surgical procedure (e.g., endoscopy, appendectomy), although the condition that leads to the procedure is an AE
- anticipated day-to-day fluctuations of pre-existing disease(s) or condition(s) (including laboratory values) present or detected at the start of the study that do not worsen
- the disease or disorder being studied, or expected progression, signs, or symptoms of the disease or disorder being studied, unless they become more severe or occur with a greater frequency than expected for the subject's condition

Confidential Page 41 of 67

8.2 Definition of a Serious Adverse Event (SAE)

An SAE is defined as any event that meets the following criteria:

- It results in death
- It is life-threatening (i.e., presents an immediate risk of death from the event as it occurred) (This criterion does not mean that the AE hypothetically might have caused death if it were more severe)
- It results in persistent or substantial disability or incapacitation (This criterion is not intended to include experiences of relatively minor medical significance, such as uncomplicated headache, diarrhea, or sprained ankle)
- It results in hospitalization
- It results in prolongation of an existing hospitalization
- It is a congenital anomaly or birth defect
- It requires medical or surgical intervention to prevent any of the above outcomes
- Other medically important condition

(Note: Important medical events that may not result in death, be life threatening, or require hospitalization may be considered an SAE when, based upon appropriate medical judgment, they may jeopardize the patient and may require medical or surgical intervention to prevent one of the outcomes listed above. Examples of such medical events include allergic bronchospasm requiring intensive treatment in an emergency room or at home, blood dyscrasias or convulsions that do not result in inpatient hospitalization, or the development of drug dependency.)

Medical and scientific judgment should be exercised in determining whether an AE is serious when considering important medical events that may not be immediately life-threatening or result in death or hospitalization, but may jeopardize the subject or may require intervention to prevent any of the other outcomes listed.

Hospitalization for elective treatment of a pre-existing condition that did not worsen from Baseline does not meet the definition of an SAE.

Admission to a hospital or prolongation of a hospitalization for social or convenience reasons (e.g., cosmetic surgery) not associated with the occurrence of an AE does not meet the definition of an SAE.

8.2.1 Serious Adverse Events That Occur Before Administration of Study Medication

Before administration of study medication, only SAEs assessed by the Investigator as related to study participation (e.g., related to study procedures or a change in existing therapy) will be transcribed onto the SAE reporting form and reported to the Sponsor via Premier Research Pharmacovigilance

8.2.2 Serious Adverse Events That Occur After Study Completion

If the Investigator becomes aware of an SAE or death that occurs in a subject within 30 days after Visit 4and that Investigator considers the event to be related to the study medication, the Investigator is obligated to report the SAE to the Sponsor.

Confidential Page 42 of 67

8.3 Collecting, Recording and Evaluating Adverse Events and Serious Adverse Events

The AE reporting period for this study begins at Screening and ends at Visit 4. All AEs that occur in trial subjects during this reporting period must be reported, without consideration to drug relatedness. In addition, any known AE that occurs subsequent to the AE reporting period that the investigator assesses as related to the study medication should also be reported as an adverse event.

The Investigator will attempt to establish a diagnosis of the event on the basis of signs, symptoms, or other clinical information. In such cases, the diagnosis, not the individual signs or symptoms, should be documented as the AE or SAE. AEs will be collected from the point the ICF is signed through EOT or Early Termination Visit.

Both total and treatment-emergent AEs will be reported. Treatment-emergent AEs are defined as those that occur after dosing of study medication until EOT or Early Termination Visit.

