4.2.9 Study Visits and Procedures

All study visit assessments will be collected on electronic case report forms (eCRF).

Safety will be monitored by observation of and direct inquiry regarding AEs at Screening, Baseline, and each post-dose visit. Subjects may experience AEs that necessitate an unscheduled visit. Situations may also arise wherein the Investigator asks a subject to report for an unscheduled visit (UNS) following the report of an AE or SAE. Additional examinations may be conducted at these visits as necessary to ensure the safety and well-being of subjects during the study. All eCRFs should be completed for each unscheduled visit. Refer to Section 8.3 for information on AE collection, recording, and reporting.

Medical history will capture all medical conditions at the Screening visit. Physical examination, 12-lead electrocardiogram (ECG), and clinical laboratory tests will be conducted as described on Appendix A, or at the discretion of the Principal Investigator.

In addition, the C-SSRS will be administered at Screening, Baseline, and all subsequent scheduled visits to assess emergent suicidal thoughts or behaviors. Vital signs (BP and HR), body weight and direct questioning to assess for sleep, appetite, mood and psychotic events will be conducted at Baseline and Visits 1 to 5. The Questionnaire for Sleep, Appetite, Mood, and Psychotic Adverse Events will be administered at Baseline and all subsequent scheduled visits.

During Visit 5, subjects who are smokers will be allowed to have up to 3 cigarette breaks.

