4.2.10.4 Visit 4 (Day 28) Abbreviated administration of serial PERMPs

The following assessments will be performed at Visit 4:

- Blood pressure and pulse (average of triplicate measurements) at pre-dose and ~3 hours post-dose
- Body weight
- Abbreviated administration of serial PERMPS at pre-dose, 0.5, 1, 2 and 4 hours post-dose. Pre-dose PERMP will be administered approximately 30 minutes prior to dosing, followed by on-site administration of AMPH ER TAB 20 mg or matching placebo by the clinic staff.

Confidential Page 32 of 67

- AISRS
- CGI-S
- "Since Last Visit" C-SSRS
- Questionnaire for Sleep, Appetite, Mood, and Psychotic Adverse Events
- AE assessment
- Concomitant medications assessment
- DB AMPH ER TAB 20 mg or matching placebo dispensing, accountability, and subject training regarding investigational drug.

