4.2.10.5 Visit 5 (Day 35) Administration of serial PERMPs

The following activities will be performed during Visit 5:

- Administration of serial PERMPs at pre-dose and at 0.5, 1, 2, 4, 8, 10, 12, 13, and 14 hours post-dose
- Physical examination
- Blood pressure and pulse (average of triplicate measurements) at pre-dose and ~3 hours post-dose
- Body weight
- On-site drug administration of AMPH ER TAB 20 mg or matching placebo
- AE assessment
- Concomitant medications assessment
- Study drug accountability and drug reconciliation

The following activities will be performed at or within 2 days of Visit 5:

- AISRS
- CGI-S
- DSST
- "Since Last Visit" C-SSRS
- Questionnaire for Sleep, Appetite, Mood, and Psychotic Adverse Events
- Resting 12-lead ECG
- Laboratory tests (see Table 4)

Table 4 Laboratory Tests at Visit 5

Biochemistry	Non-fasting random serum glucose
	Total bilirubin
	Blood urea nitrogen (BUN)
	Creatinine with estimated glomerular filtration rate (eGFR)

Confidential Page 33 of 67

	Alkaline phosphatase
	Calcium
	Lactate dehydrogenase (LD)
	Aspartate aminotransferase [AST (SGOT)]
	Alanine aminotransferase [ALT (SGPT)]
	Serum electrolytes (sodium, potassium, and chloride)
	Gamma glutamyl transpeptidase (GGT)
Hematology	Complete blood count (CBC) with differential:
	White blood cell count (WBC) with differential
	Hemoglobin
	Hematocrit
	 Red blood cell count (RBC) to include indices
	Platelet count
Immunohematology:	Urine hCG (females only)
Urinalysis	Specific gravity
•	Urine color
	Appearance
	Bilirubin
	pH
	Leukocytes
	Nitrites
	Protein
	Glucose
	Ketones
	Blood
	Microscopic examination
	Note: microscopic examination will only be performed when any of the following
	urinalysis tests are reported abnormal (i.e., outside of normal ranges):
	leukocyte, nitrite, protein, and/or blood. The microscopic examination will be
	conducted on the same urine sample as the abnormal urinalysis test.

• Drug of Abuse Screening Test (see Table 5)

Table 5 Drugs of Abuse Screening Test at Visit 5

Drugs of Abuse:	Barbiturates
	Benzodiazepines
	Cannabinoids
	Cocaine
	Methadone
	Opiates
	Phencyclidine
	Tricyclic antidepressants

For all activities performed, the results are to be recorded in the eCRF.

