8.3.1 Assessment of Adverse Events and Serious Adverse Events

The investigator is responsible for the detection and documentation of events meeting the criteria and definition of an AE or SAE described previously. At each visit, the subject will be allowed time to spontaneously report any issues since the last visit or evaluation. The investigator will then monitor and/or ask about or evaluate AEs using nonleading questions, such as

- * "How are you feeling?"
- * "Have you experienced any issues since your last visit?"
- * "Have you taken any new medications since your last visit?"

Any clinically relevant observations made during the visit will also be considered AEs.

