9.3.6.1 Adverse Events

All AEs will be coded using Medical Dictionary for Regulatory Activities (MedDRA) Version 20.0. Treatment-emergent AEs, any AEs recorded during the study at least one dose of study medication, will be summarized and categorized by severity and relationship to the investigational drug. If a subject has more than one occurrence of the same AE, he/she will be counted only once within that preferred term in the summary tables. The most severe occurrence of an AE, as well as the most extreme relationship of the AE to the study procedures or investigational drug, will be indicated in cases of multiple occurrences of the same AE. Serious adverse events and AEs of special interest, which will be defined in the SAP, will also be summarized separately. All AEs will be presented in a listing. Additionally, listings of SAEs and AEs leading to discontinuation will be generated. All SAEs will be evaluated to determine whether they are Unexpected Adverse Reactions.

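### Adverse event reporting is said to end at Visit 4, although dosing and a scheduled AE assessment continue to Visit 5, and the alternative end point (EOT) is not defined for completers

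*Combined protocol and SAP*

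**What the plan says.** Section 8.3 of the protocol gives two different ends to AE capture. Its opening sentence reads "The AE reporting period for this study begins at Screening and ends at Visit 4", and the duty to report every AE regardless of relationship is tied to that period. Further on, the same section says "AEs will be collected from the point the ICF is signed through EOT or Early Termination Visit", and then "Treatment-emergent AEs are defined as those that occur after dosing of study medication until EOT or Early Termination Visit".

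The visit schedule runs past Visit 4:

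- Section 4.2.10.4 lists for Visit 4 (Day 28): "DB AMPH ER TAB 20 mg or matching placebo dispensing, accountability, and subject training regarding investigational drug".
- Section 4.2.10.5 lists for Visit 5 (Day 35): "On-site drug administration of AMPH ER TAB 20 mg or matching placebo". An AE assessment is on the same list, and Appendix A marks adverse events at Visit 5.
- Section 4.2.9: "Safety will be monitored by observation of and direct inquiry regarding AEs at Screening, Baseline, and each post-dose visit".
- Section 8.3.1: "At each visit, the subject will be allowed time to spontaneously report any issues since the last visit or evaluation".

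Three further places bear on the end point. Section 8.2.2, whose heading concerns SAEs after study completion, counts 30 days from Visit 4. Section 9.3.6.1 defines the analysed events as "Treatment-emergent AEs, any AEs recorded during the study at least one dose of study medication, will be summarized", with no end date beyond the study itself. Section 8.4 refers the reader to a Section 11.2 for the observation period, but Section 11 has no subsections.

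**The concern.** A site cannot follow both the Visit 4 sentence and the Visit 5 schedule. Visit 4 ends neither treatment nor the study. The week after it is spent at 20 mg, the highest dose in the trial, and the Visit 5 laboratory tests, ECG and directed questionnaire on sleep, appetite, mood and psychotic events come at the end of that week. Section 8.1 requires any laboratory abnormality judged clinically significant to be reported as an AE, so some of what is collected around Visit 5 is meant to become AE data.

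Safety is one of the trial's two objectives. If a site stopped routine reporting at Visit 4 and afterwards recorded only related events, the AE tables would mix all-cause capture before Visit 4 with relatedness-filtered capture after it. Section 9.3.6.1 summarises treatment-emergent events by relationship, so the filter would affect those tables directly. Separately, whoever programs the treatment-emergent flag has no unambiguous last day for subjects who complete the study.

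**Working it through.** There is no figure of the plan's own to reproduce. The check compares the passages and then does day arithmetic on nominal visit days.

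**Inputs.** Visit 3 = Day 21 (Section 4.2.10.3). Visit 4 = Day 28 (4.2.10.4). Visit 5 = Day 35 (4.2.10.5). Exposure before Visit 5 is 35 (± 3) days, of which 14 (± 3) are at 20 mg; visit windows are ± 3 days (9.3.8). The related-SAE window is 30 days from Visit 4 (8.2.2). Some Visit 5 procedures have a 2-day allowance (4.2.10.5).

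**Treatment time after the stated cut-off**

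- Visit 4 to Visit 5: 35 − 28 = 7 days.
- Share of planned treatment: 7/35 = 20%.
- Time at 20 mg: 35 − 21 = 14 days; share after Visit 4: 7/14 = 50%.
- Range of the gap, if the ± 3 days applied to each visit independently: (35 − 3) − (28 + 3) = 1 day, to (35 + 3) − (28 − 3) = 13 days.

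**The Section 8.2.2 window**

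- As written: 28 + 30 = Day 58.
- Counted from Visit 5: 35 + 30 = Day 65.
- Days of the written window that fall after Visit 5: 58 − 35 = 23 of 30.
- If the anchor were a Visit 5 procedure done 2 days after the visit: 35 + 2 = Day 37, and 37 + 30 = Day 67. This assumes the allowance runs after the visit; the text does not say before or after.

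**Does EOT settle the end point?** Four places were compared.

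- Section 8.3 names EOT and the Early Termination Visit as alternatives, as if they were two events.
- Section 6.1 is the only place that spells out EOT, and there it means early termination.
- Section 4.2.10.6 limits the Early Termination Visit to subjects who withdraw before completing Visit 5.
- Appendix A gives EOT a column separate from Visit 5. Its key explains EOS and ET but not EOT, and the list of abbreviations omits EOT.

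On the only expansion given, a completer never reaches EOT. Section 9.3.6.1 does not supply the missing date, and the Section 8.4 cross-reference leads nowhere.

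**Is Visit 4 an isolated slip?** No. Section 6.2 also uses Visit 4 as its anchor, and Section 7 describes a 4-week double-blind phase, whereas Sections 3.5 (contraception) and 6.2.1 (alcohol) count from Visit 5. The pattern is consistent with text not updated for a fifth visit, but that cause is an inference.

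**The case against.** The strongest reply is that the rest of the protocol leaves little doubt about intent. AE inquiry is ordered at every post-dose visit, an AE assessment is on the Visit 5 list, and the Appendix A grid marks it. Section 8.6 requires every SAE during the study to be reported whatever its relationship, and Section 8.3 keeps related AEs reportable after the period with no end date. Section 8.5 treats the last scheduled visit as the boundary for following non-serious events. What remains exposed is unrelated, non-serious AEs at a site that disregards its own Visit 5 checklist. All of this stands. It limits the consequence but does not remove the contradiction.

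Some narrower points also stand. The percentages describe time and show no quantity of data lost. A related event on Days 59 to 65 would still be reportable as an AE under Section 8.3, so only the explicit SAE duty in Section 8.2.2 shifts. Section 9.3.6.1 is looser than Section 8.3 and does not state a competing date. The protocol also defers analysis detail to a separate SAP, which might define the treatment-emergent window.

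The argument that EOT in Section 8.3 most naturally means the completers' end of treatment is reasonable as a guess at intent. It conflicts with the only expansion of the term, so it is not a definition.

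**Conclusion.** The concern holds and should be fixed. As written, the rule for reporting all AEs stops one visit before dosing and the last scheduled AE assessment. The size is nominally 7 of 35 treatment days and half the time at 20 mg; the calendar gap could be 1 to 13 days if both visit windows applied independently. The Section 8.2.2 window nominally closes 7 days earlier than it would if counted from Visit 5 (Day 58 against Day 65).

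Loss of events is possible, not established: it depends on a site acting on the Visit 4 sentence against the schedule, and it concerns unrelated, non-serious AEs. The lack of a defined treatment-emergent end point for completers does not depend on site behaviour. It is present in the text, subject to whatever a separate SAP may specify. Sample size and power are not affected.

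**What to change.** - **Section 8.3:** end the AE reporting period at Visit 5, including Visit 5 procedures done within the 2-day allowance, or at Early Termination. The allowance should be covered because laboratory tests, ECG and the directed questionnaire may fall within it. State whether it runs before or after the visit.
- **Section 8.2.2:** count the 30 days from that same point.
- **EOT:** define it for completers in the text, the list of abbreviations and the Appendix A key, or replace it.
- **Sections 8.3 and 9.3.6.1:** use one treatment-emergent definition with that end point.
- **Section 8.4:** correct the reference to Section 11.2.
- **Sections 6.2 and 7:** reconcile the Visit 4 anchor and the 4-week wording with the five-visit schedule. No view is taken here on the medication rule in Section 6.2.

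The cost is text correction only. The Visit 5 AE assessment is already scheduled, so no visit or procedure is added.

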3.6 Subject Withdrawal Criteria

Within the provisions of informed consent and good clinical judgment with respect to the subject's safety, every attempt should be made to have subjects complete the study. The following are possible reasons to terminate the participation of any subject from the study:

Confidential Page 25 of 67

- Signs and symptoms of intolerance to the study medication.
- A treatment-related, serious adverse event (SAE) is observed.
- The subject is grossly non-compliant, as determined by the Investigator.
- Continued participation, in the opinion of the Investigator, is no longer in the best interest of the subject.
- The subject wishes to withdraw for any reason.
- Unblinding of the Investigator, site personnel performing assessments, or subject to a subject's treatment assignment.

Subjects will be encouraged to adhere to the protocol and complete all required assessments for the study. A subject may also be discontinued from the study for any of the following medical and/or administrative reasons:

- Pregnancy
- At the discretion of the Investigator at any time
- At the subject's request
- Occurrence of a Treatment Emergent Adverse Event (TEAE) or considerable worsening of an AE that represents an unacceptable risk to the subject and when continued participation in the investigational study is not warranted, in the judgment of the Investigator or the Sponsor. The Investigator must follow the subject until the AE resolves or satisfactorily stabilizes.

Any enrolled subjects desiring to discontinue prior to study completion should be encouraged to continue in the study and adhere to the protocol and subsequent regularly scheduled safety and effectiveness evaluations. Subjects who are discontinued outside of any scheduled visit will be encouraged to complete the final study visit at the time of withdrawal. Subjects who are discontinued during a scheduled visit will be encouraged to complete all assessments for both that study visit and the final study visit at the time of withdrawal. A subject who withdraws following study drug administration will not be replaced in their cohort.

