4.2.10 Study Periods

Study duration is up to 11 weeks consisting of the following:

- Screening (up to 6 weeks prior to Baseline)
- Baseline

Confidential Page 28 of 67

- Visits 1 to 3 (DB Titration)
- Visit 4 (Abbreviated administration of serial PERMPs)
- Visit 5 (Administration of serial PERMPs)

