6.2.1 Prohibited Concomitant Medications

Any stimulant (e.g., methylphenidate, dexmethylphenidate, amphetamine, and dextroamphetamine) should be discontinued 7 days prior to Baseline. The following medications are prohibited during the study:

Selective serotonin reuptake inhibitors (SSRIs) (e.g., paroxetine)

Serotonin and norepinephrine reuptake inhibitors (SNRIs) (e.g., desvenlafaxine, duloxetine, venlafaxine – with the exception of fluoxetine which is restricted for 30 days prior to Baseline) MAOIs

Mood stabilizers (e.g., lithium, valproate, quetiapine)

Antipsychotics (e.g., risperidone, olanzapine)

Anticonvulsants (e.g., phenobarbital, phenytoin, primidone)

Sedative hypnotics, except melatonin

Anticoagulants

Halogenated anesthetics

Tricyclic antidepressants

Atomoxetine

Guanfacine

Clonidine

CYP2D6 inhibitors (e.g., paroxetine and fluoxetine, quinidine, ritonavir)

Fentanyl, tramadol, tryptophan, buspirone, St. John's Wort

Gastrointestinal acidifying agents (e.g., guanethidine, reserpine, glutamic acid HCl, ascorbic acid)

Urinary acidifying agents (e.g., ammonium chloride, sodium acid phosphate, methenamine salts

Decongestants (e.g. oxymetazoline, phenylephrine, pseudoephedrine)

Sedating antihistamines (e.g. alimemazine, chlorphenamine, clemastine, cyproheptadine, hydroxyzine, promethazine)

Acetaminophen is permitted for control of fever or pain if needed. Short courses of prescription and non-prescription medications needed for treatment of acute illnesses such as the common cold, viral illnesses, and ear infections are permitted as long as these do not contain medications listed above. Ongoing antihypertensive treatment will be assessed by the Investigator and the Sponsor.

Confidential Page 38 of 67

Alcohol consumption will be restricted form Baseline to 24 hours after Visit 5.

All concomitant medications must be recorded on the Concomitant Medication CRF.

The Investigator should contact the Medical Monitor for a written Note to File or Memo to File for evidence that the Sponsor is aware of a chronic or acute medication and a judgment on whether the subject may continue in the study.

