8.4 Documentation

All AEs that occur within the period of observation for the study must be documented in the CRF with the following information, where appropriate. (The period of observation for the study is described in Section 11.2.)

- AE name or term
- When the AE first occurred (start date and time)
- When the AE stopped (stop date and time or an indication of "ongoing")
- Severity of the AE
- Seriousness (hospitalization, death, etc.)
- Actions taken; may consist of:
 - O **Dose increased**: An indication that a medication schedule was modified by addition; either by changing the frequency, strength, or amount.
 - o **Dose not changed**: An indication that a medication schedule was maintained.
 - O Dose reduced: An indication that a medication schedule was modified by subtraction, either by changing the frequency, strength, or amount.
 - o **Drug interrupted:** An indication that a medication schedule was modified by temporarily terminating a prescribed regimen of medication.
 - o **Drug withdrawn**: An indication that a medication schedule was modified through termination of a prescribed regimen of medication.
 - o **Not applicable:** Determination of a value is not relevant in the current context.
 - o **Unknown**: Not known, not observed, not recorded, or refused.
- Outcome
- Investigator opinion regarding the AE relationship to the IP(s)

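### Neither of the two treatment-emergent AE definitions says how to count an AE that starts before the first dose and worsens after it

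*Combined protocol and SAP*

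**What the plan says.** The protocol defines a TEAE twice.

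- Section 8.3: "Treatment-emergent AEs are defined as those that occur after dosing of study medication until EOT or Early Termination Visit". The test is when the event occurs.
- Section 9.3.6.1: "Treatment-emergent AEs, any AEs recorded during the study at least one dose of study medication, will be summarized and categorized by severity". The sentence has lost a word or more, but its test is recording, not onset.

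The period before the first dose lies inside AE collection. Section 8.3 says "AEs will be collected from the point the ICF is signed through EOT or Early Termination Visit". Section 4.2.10 allows up to 6 weeks of Screening, section 6.2.1 says stimulants "should be discontinued 7 days prior to Baseline", and section 3.1 starts dosing the day after Baseline.

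Three other sections bear on worsening.

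- Section 8.1 lists as an example of an AE "exacerbation of a chronic or intermittent pre-existing condition, including either an increase in frequency or intensity of the condition". Its list of things that are not AEs exempts day-to-day fluctuation of conditions present or detected at study start only if they do not worsen.
- Section 8.4 sets the content of the AE record. The onset item is "When the AE first occurred (start date and time", and severity is a separate item. It gives no instruction for an ongoing AE that changes grade.
- Section 3.6 includes among the reasons for discontinuation "Occurrence of a Treatment Emergent Adverse Event (TEAE) or considerable worsening of an AE that represents an unacceptable risk to the subject".

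**The concern.** Subjects can reach the first dose with an AE already open. AEs are assessed at Screening and Baseline. The Appendix B questionnaire, given at Baseline, asks about changes in sleep, appetite, mood and unusual experiences since the last visit, which takes in the stimulant washout. These are also the event types that the trial sets out to track on amphetamine.

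If such an event worsens on study drug and the record keeps its pre-dose onset, the 8.3 rule leaves it out of the TEAE count. The tables by severity and by relationship in 9.3.6.1 are built on TEAEs, and safety and tolerability is a stated objective (section 2.2). What is at stake is whether those tables treat the same clinical course in the same way in every subject and at each of up to 3 sites.

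**Working it through.** The plan states no figure to reproduce, so the check is to apply the definitions to cases.

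The inputs are the 8.3 rule (onset after dosing), the 9.3.6.1 rule (recording), the 8.4 onset item, and the schedule in 3.1, 4.2.10 and 6.2.1. Because 9.3.6.1 is garbled, two readings are tried: (A) first recorded after at least one dose; (B) recorded at any time in a subject who took at least one dose.

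| Case | 8.3 | 9.3.6.1 (A) | 9.3.6.1 (B) |
|---|---|---|---|
| 1. Opened at Baseline, worsens after dosing, site keeps one record | not TEAE | not TEAE | TEAE |
| 2. As 1, but site opens a new record dated at the worsening | TEAE | TEAE | TEAE |
| 3. As 1, but the new record carries the first onset date | not TEAE | TEAE | TEAE |
| 4. Began before dosing, first reported at Visit 1, never worsens | not TEAE | TEAE | TEAE |
| 5. Opened at Baseline, never worsens | not TEAE | not TEAE | TEAE |

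Three things follow.

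1. Cases 1 to 3 are the same clinical event. Under 8.3 its status depends on how the site fills in the form, and 8.4 does not settle that. Its request for the first occurrence points towards case 1 or case 3.
2. The broader 9.3.6.1 wording does not supply the missing rule. Where it picks up a worsened event, it also picks up events that never worsened (case 4 under A; cases 4 and 5 under B).
3. Sections 8.3 and 9.3.6.1 disagree on cases 3 and 4 under reading A, and on cases 1, 3, 4 and 5 under reading B. They need to be reconciled whatever is decided about worsening.

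*Opportunity.* The pre-dose collection period is up to 6 × 7 = 42 days, including the 7-day washout. Planned exposure before Visit 5 is 35 (± 3) days (section 9.3.8).

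*Scale per subject.* Section 9.1 plans about 108 subjects. Assuming equal allocation, which the text does not state, there are 108 / 2 = 54 per arm. One misclassified subject is then 1 / 54 = 1.9 percentage points of that arm's incidence for the term concerned. No AE rate is given, so the number of such subjects cannot be computed.

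**The case against.** The strongest reply is that the protocol already treats worsening as an AE. Section 8.1 names exacerbation of pre-existing conditions, and its exemption is limited to conditions that do not worsen. Section 8.3.1 adds that clinically relevant observations at a visit count as AEs. A site reading these together could enter the worsening as a new event after dosing, which satisfies 8.3. The counting rule in 9.3.6.1 already allows more than one record of the same AE. This stands as a possible route. It is not an instruction, and it does not clearly reach an acute AE first opened during Screening or washout.

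It also stands that the data are not lost. Total AEs (8.3), the frequencies by system organ class and preferred term (9.3.6), the listings of all AEs and of AEs leading to discontinuation (9.3.6.1), the withdrawal table (9.3.1), the questionnaire summary (9.3.6.3) and vital-sign changes (9.3.6.5) would still show these subjects. None of them replaces a TEAE table by severity and relationship.

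Section 9 promises a detailed SAP, whose text is not in the supplied document. A worsening clause there cannot be ruled out, but neither can it be credited. A later SAP also could not recover a date of worsening that was never captured.

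Some stronger readings are tempting, but the documents do not support them.

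- *Section 3.6 shows that worsening is not a TEAE.* It is a list of withdrawal reasons. It does not say that the AE began before dosing, and worsening of an AE that began on drug fits it equally well.
- *Section 8.4 allows one severity per AE.* It asks for severity; it neither limits an event to one grade nor bars a second record.
- *A discontinuation for worsening would go unseen.* The discontinuation listing and the withdrawal table would show it.
- *The drug-placebo difference is understated.* Open AEs can worsen on placebo too, so the net direction depends on a between-arm contrast that the documents do not give.
- *About 1 to 3 subjects per arm are affected.* That follows if 10-20% start dosing with an open AE and 20-30% of those worsen: 0.10 × 0.20 = 2% and 0.20 × 0.30 = 6% of 54. Neither pair of rates has a source in the documents.

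**Conclusion.** The point holds as a defect of definition. Two TEAE wordings are in force, they can classify the same event differently, and neither covers worsening of an AE that predates the first dose. Such events can be left out of the TEAE severity and relationship summaries, or counted according to site habit.

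The conclusion rests on applying 8.3 as written to the onset date that 8.4 collects, and on the absence of any worsening rule elsewhere in the supplied text. The size and direction of any effect on the between-arm comparison are undetermined. The efficacy analyses are not touched. The correction is worth making because it costs little and because the date of worsening has to be captured at the time.

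**What to change.** Put one definition in both 8.3 and 9.3.6.1: a TEAE is an AE that starts, or increases in severity or becomes serious, on or after the first dose of study drug. In 8.4, state that a pre-dose AE that worsens after dosing is entered as a new record, with the date and time of the worsening as its start. The once-per-preferred-term rule in 9.3.6.1 can stay, so a subject with two records for the same term is still counted once.

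The cost is a sentence or two in each section, one CRF completion instruction, and possibly slightly higher TEAE counts.
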